11.4.3. Urinalysis

The results will only be displayed in a listing.

11.4.4. Coagulation

The results will only be displayed in a listing.

11.4.5. Fasting Lipid Panel

Fasting lipid panel includes total cholesterol, low-density lipoprotein cholesterol (LDL-C), high-density lipoprotein cholesterol (HDL-C), and triglycerides. Lipid profiles will be described by concentration of the lipids at scheduled visits and change from baseline by treatment arm for Phase 2. The proportion of subjects with clinically meaningful post-baseline increase in lipids will be summarized based on criteria presented in [Table 6](#) for both Phase 1b and Phase 2.

Table 6: Fasting Lipid Changes of Interest

Laboratory Test	Parameters for any value and the last value
LDL cholesterol	>ULN and >10% increase from BL
LDL-C/HDL-C ratio	>3.5 and >10% increase from BL

11.4.6. Cardiac Markers

Cardiac markers include troponin T. The results will only be displayed in a listing.

11.4.7. Females of Childbearing Potential

The results will only be displayed in a listing.

11.5. Vital Sign Measurements

Evaluation of vital signs includes recording height (only at screening), weight, temperature, systolic blood pressure (SBP), diastolic blood pressure (DBP), pulse rate, and respiratory rate at scheduled visits.

Vital sign measurements will be listed for each subject and by scheduled visit. Descriptive statistics for vital signs (except height), both observed values and changes from baseline, will be summarized by treatment arm for Phase 2.

In addition, a shift table will show the number of subjects with high, normal, low values by treatment arm and by parameter at each visit. Normal ranges are defined as below (anything lower than the low limit is a low value, anything higher than the upper limit is a high value):

- SBP 100-140 mmHg
- DBP 60-90 mmHg
- Pulse 60-100 beats per minute (bpm)
- Respiration 12-20 bpm

11.6. Electrocardiograms

Electrocardiogram (ECG) parameters include heart rate, PR interval, QRS duration, RR interval, QT, QTc Fridericia value (QTcF) and QTc Bazett value (QTcB). QTcB is not recorded in the eCRF page and will be calculated in the following way: $QTcB = QT (ms) / \sqrt{RR (ms) / 1000}$.

Recorded values and of ECG parameters and change from baseline values will be summarized at each time point by treatment arm for Phase 2 only.

In addition, at baseline and maximum post-baseline visits, the proportion of subjects having absolute QTcF and QTcB intervals of the following categories will be presented:

- ≤ 480 ms
- > 480 to ≤ 500 ms
- > 500 ms

At maximum post-baseline visits, the proportion of subjects who have an increase from baseline in QTcF and QTcB intervals of the following categories will be presented:

- ≤ 30 ms
- > 30 to ≤ 60 ms
- > 60 ms

The overall ECG interpretation will be summarized by presenting the shift from baseline to worst by treatment arm for all cycles. The overall ECG interpretation will be displayed in cross-tabulations for each treatment.

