#### Phase 1b (Dose-finding and AG-120 Expansion) and Phase 2 AG-221 Radomomized Stage

AG-120 or AG-221 will be dispensed on Day 1 of each treatment cycle, with sufficient IP to complete a 28-day cycle. Subjects should be instructed to open AG-120 or AG-221 packaging as close as possible to when they are going to take AG-120 or AG-221, inspect each AG-120 or AG-221 tablet and only take tablets that are totally intact (subjects should be instructed to return any tablet not totally intact to the clinic).

Subjects should be instructed to take their daily dose at approximately the same time each day  $\pm$  6 hours. Each dose should be taken with a glass of water and consumed over as short a time as possible. Subjects should be instructed to swallow tablets whole and to not chew the tablets. Fasting is required for 2 hours prior to and 1 hour following AG-221 administration. Water is allowed during fasting. Fasting is not required for AG-120 administration.

All efforts should be made to administer AG-120 or AG-221 on all of the scheduled days of each 28-day treatment cycle. A dose missed earlier in a day can be made up later that day as long as it is taken within 6 hours after the missed dose. If more than 6 hours have elapsed, then that dose should be omitted, and the subject should resume treatment with the next scheduled dose. Any missed doses should be documented in the subject diary and not be taken beyond the last scheduled day of AG-120 or AG-221 administration, but should be returned by the subject for drug accountability.

If vomiting occurs shortly after a dose of AG-120 or AG-221 administrated, that dose should not be made up later that day. The subject should continue with the dosing schedule on the next day and inform the investigator about the vomiting event at the next visit and document this in the subject diary.

In order to optimally benefit from the treatment, investigators should aim to treat patients for at least 6 cycles, although patients can be discontinued from protocol earlier if they demonstrate unacceptable toxicity or relapse after CR or PR, transformation to AML, or disease progression.

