**Non-hematologic toxicities**

Non-hematologic toxicities include all clinically significant non-hematologic toxicities of  $\geq$  Grade 3 with the exception of  $\geq$  Grade 3 blood bilirubin increases in subjects with a UGT1A1 mutation. In subjects with a UGT1A1 mutation, blood bilirubin increases of  $> 5 \times$  ULN may be considered clinically significant.

QT prolongation

The discussion of the emergency management of torsade de pointes and its hemodynamic consequences is beyond the scope of this guideline.

[REDACTED] As of 01 May 2015, 6 (10.5%) of 57 subjects in Study AG120 C 001 have experienced QT prolongation while receiving AG 120. QTc interval has been observed in dogs at relatively low doses of AG-221. Prolonged QTc interval has not been seen in other animal species at high doses.

Subjects may be at increased risk for the development of QT prolongation when treated with AG 120 administered with fluoroquinolones, azole antifungal agents, or serotonin (5-HT3) antagonists. Investigators need to be vigilant; refrain from administering concomitant medications associated with QT prolongation, and if no other therapeutic options are available, monitor subjects receiving AG-120 with the combination of these drugs, and evaluate ECG and electrolytes (including potassium, magnesium, and calcium) particularly in subjects presenting with nausea, vomiting, or diarrhea.

Please refer to the [AG-120 Investigator's Brochure](#) for detailed information concerning the available pharmacology, toxicology, drug metabolism, clinical studies, and adverse event profile of AG-120.

Subjects who experience prolongation of the heart-rate corrected QT interval, Fridericia's correction (QTcF) to > 480 msec (Grade  $\geq$  2) while treated with AG-120 or AG-221, should be promptly evaluated for causality of the QTc prolongation and managed according to the following guidelines:

- Levels of electrolytes (potassium, calcium, and magnesium) should be checked and supplementation given to correct any values outside the normal range.
- Concomitant therapies should be reviewed and adjusted as appropriate for medication with known QT prolonging effects.

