### 7.3. Method of Treatment Assignment

In the dose-finding phase, each dose cohort will initially enroll 3 subjects. The dose of AG-120 and AG-221 for each subject will be based on the assigned cohort. Azacitidine will be administered at 75 mg/m^2/day SC for 7 days of each 28-day cycle across all cohorts.

Once the RCD is determined, enrollment will begin in Phase 1 expansion for IDH1 subjects or in Phase 2 of the study for IDH2 subjects. As noted in Section 3.1.2, subjects with IDH2 mutation will be randomized to receive oral AG-221 + SC azacitidine (Arm 1) versus SC azacitidine (Arm 2) in a 2:1 ratio. Arms 1 will randomize a minimum of 66 subjects and 2 will randomize a minimum of 33 subjects (99 subjects total in both arms).

Subjects in the Phase 2 segment will be stratified by primary (ie, de novo) or secondary (progression of MDS or myeloproliferative neoplasms [MPN], or therapy-related) AML according to the WHO classification ([Appendix B](#)).

An IWRS will be used to track subject enrollment / randomization to the treatment arms and dosing. Assignment of drug kit will be performed by contacting IWRS at Day 1 of each cycle.

Celgene trial staff will review and verify documented specific eligibility criteria for all screened subjects prior to allowing enrollment of subjects via the IWRS but enrollment / randomization is ultimately the responsibility of the investigator.

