## 9.7. Safety Analysis

All safety analyses will be performed on the safety population.

Adverse events will be summarized by Medical Dictionary for Regulatory Activities (MedDRA) system organ class and preferred term. Separate tabulations will be produced for all treatment-emergent AEs (TEAEs), treatment-related AEs (those considered by the investigator as at least possibly drug related), SAEs, discontinuations due to AEs, and AEs with at least a Grade 3 severity. By-subject listings will be provided for deaths, SAEs, DLTs, and AEs leading to discontinuation of treatment.

Clinical laboratory results will be listed and summarized descriptively by dose group, which will also include a display of change from baseline. Laboratory values outside of the normal ranges will be identified. Clinically significant laboratory abnormalities that meet Grade 3 or Grade 4 criteria according to the CTCAE version 4.03 will be listed and summarized. Graphical displays of select laboratory parameters over the course of the study may be provided where useful to assist in the interpretation of results.

Descriptive statistics will be provided for ECG intervals and vital sign measurements presented as both actual values and changes from baseline to the post-baseline visit and to the last visit in the study. Electrocardiograms will also be analyzed for QTc intervals, QTc > 480 and > 500, and increase > 30 and > 60 msec.

Tolerability of the study drug will be assessed by summarizing the number of dose interruptions and dose reductions. Reasons for dose interruption and dose reductions will be listed by subject and summarized.

Subjects in Phase 1b with the same dose level may be pooled with those in Phase 2 for safety presentation as appropriate.

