5. GENERAL STATISTICAL CONSIDERATIONS

5.1. Reporting Conventions

The following reporting conventions apply generally to tables, listings, and figures:

- Data from all study centers will be combined for analysis;
- In general, analyses for Phase 1b subjects will be done by AG-120 + AZA and AG-221 + AZA and by dose cohort in dose-finding, total in dose-finding, dose cohort in expansion (only for AG-120 + AZA), and total for AG-120 + AZA. For Phase 2, AG-221+AZA versus pooled AZA alone will be compared.
- P-values will be rounded to 4 decimal places; P-values that round to 0.0000 will be presented as '<0.0001' and p-values that round to 1.000 will be presented as '>0.9999
- Confidence intervals (CIs) will be presented as two-sided 95% CIs unless specified differently in specific analysis;
- Summary statistics will consist of the number and percentage of subjects (or cycles, if appropriate) in each category for discrete variables, and the sample size, mean, median, standard deviation, first quartile (Q1), third quartile (Q3), minimum, and maximum for continuous variables;
- All mean and median values will be formatted to one more decimal place than the measured value. Standard deviation values will be formatted to two more decimal places than the measured value;
- All percentages will be rounded to one decimal place. The number and percentage of responses will be presented in the form XX (XX.X%), where the percentage is in the parentheses. In case of zero frequency, the percentage will not be displayed;
- All listings will be sorted for presentation in order of treatment arm, study center, subject, and date/time of procedure or event and will be presented separately for each phase. Subjects who are screened but not randomized will be listed separately as a non-randomized group;
- All analysis and summary tables will have the analysis population sample size (i.e., number of subjects);
- The day of the first dose of any study drug will be defined as Day 1.
- Unless noted otherwise, baseline value will be defined as the last non-missing value prior to the start of study treatment on Day 1 of Cycle 1. For subjects who are randomized but not treated, the baseline will be the assessment value on or prior to randomization date.
- To summarize efficacy/safety data by visit, the post-baseline results will be summarized by the scheduled visit or the derived visit as appropriate.
- Calculation of Cycles:

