11. SAFETY ANALYSIS

All analyses of safety data will be conducted using the safety population unless otherwise specified, separately for Phase 1b and Phase 2. Safety summaries will be provided by dose cohort (Phase 1b), and treatment arm (Phase 2), and overall (Phase 1b and Phase 2 separately).

For summaries of safety data, the treatment period is defined as follows:

date of first dose through date of last dose + 28 days.

No inferential statistical analyses will be conducted on the safety data.

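### SAP 11.6 confines by-visit ECG summaries to Phase 2, so AG-120, given only in Phase 1b, loses the QTcF change summary that Protocol 9.7 plans without a phase limit (minor)

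*SAP*

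**What the plan says.** **Protocol 9.7** states: "Descriptive statistics will be provided for ECG intervals and vital sign measurements presented as both actual values and changes from baseline", the changes being those to the post-baseline visit and to the last visit. It names no phase. It separately asks for QTc above 480 and 500 ms and increases above 30 and 60 ms. The Statistical Methods part of the Protocol Summary also plans descriptive statistics for continuous data in Phase 1b.

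**SAP 11.6** lists QTcF and QTcB among the ECG parameters and then limits the by-time-point output: "change from baseline values will be summarized at each time point by treatment arm for Phase 2 only". Three further outputs carry no phase limit: the absolute QTc categories, the increase categories ("At maximum post-baseline visits, the proportion of subjects who have an increase from baseline in QTcF and QTcB intervals") and the shift in overall ECG interpretation.

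**Where AG-120 is given.** Protocol 7.3 says that, once the recommended combination dose is set, "enrollment will begin in Phase 1 expansion for IDH1 subjects or in Phase 2 of the study for IDH2 subjects". SAP section 2 names the Phase 2 arms as AG-221 100 mg + AZA and AZA alone.

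**The QT signal.** In the QT prolongation text of Protocol 7.2.2.3.2: "6 (10.5%) of 57 subjects in Study AG120 C 001 have experienced QT prolongation" while on AG-120.

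**The concern.** Taken together, the two documents drop a planned safety summary for one drug entirely. AG-221 still gets by-visit QTcF in Phase 2. AG-120 has no Phase 2 arm, and the pooling of equal dose levels across phases that Protocol 9.7 allows cannot help it. The SAP gives no reason for the narrowing.

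AG-120 is also the drug for which the protocol reports clinical QT prolongation. The ECGs will exist: Protocol Table 4 schedules them on Days 1 and 15 of Cycles 1 and 2 and on Day 1 of later cycles. C1D15 and C2D1 are also AG-120 PK sampling days in the expansion (Protocol Table 6).

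At stake is a description of how far QTcF moves, how variable the change is and when it occurs, when the change is too small to show clearly in threshold tables.

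**Working it through.** The plan states no figure on this point, so there is nothing to reproduce. The check has a textual part and a numerical part.

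**1. Does other SAP text restore the summary?**
- SAP 11 has a general rule: "Safety summaries will be provided by dose cohort (Phase 1b), and treatment arm (Phase 2), and overall". It names no ECG output, and the specific limit in 11.6 narrows it.
- SAP 5.1 provides the columns that would be needed, "dose cohort in expansion (only for AG-120 + AZA), and total for AG-120 + AZA", but it sets a layout and does not add an output.
- SAP 11.4 gives laboratory data a descriptive summary with change from baseline by Phase 1b dose cohort, although the by-visit tables in 11.4.1, 11.4.2 and 11.4.5 are for Phase 2. ECG has no matching Phase 1b sentence.
- SAP section 11.2 and sections 14 to 16 are not in the text available, so the finding is limited to what can be read.

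**2. What do the retained tables show?**

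Inputs from the documents:
- n = 15 + 3 = 18 AG-120 subjects at the recommended dose (Protocol 9.3).
- k = 5 scheduled post-baseline ECGs through C4D1: C1D15, C2D1, C2D15, C3D1, C4D1 (Protocol Table 4).
- k = 7 through Cycle 6, since "investigators should aim to treat patients for at least 6 cycles" (Protocol 7.2.1.1), and k = 11 through Cycle 10.

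Assumed, because the documents give no QTcF variability: a single change from baseline has SD 15, 20 or 25 ms, and baseline and post-baseline readings are independent normal with equal variance.

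For a common shift δ, with τ = SD/√2:

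P(max change > 30) = 1 − ∫ φ(b) · Φ((30 − δ)/τ + b)^k db

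Expected number of 18 subjects above 30 ms, k = 5:

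| Shift | SD 15 | SD 20 | SD 25 |
|---|---|---|---|
| 0 ms | 1.5 | 3.8 | 5.9 |
| 10 ms | 4.9 | 7.5 | 9.1 |
| 20 ms | 10.2 | 11.6 | 12.4 |
| 30 ms | 15.0 | 15.0 | 15.0 |

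A shift of 20 to 30 ms is plain in the retained table. A 10 ms shift also moves the count at a given SD, by 3.2 to 3.7 subjects, but the sampling SD of such a count is about 1.2 to 2.1 subjects.

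The count also rises with follow-up alone. With no shift and SD 20 it is 3.8, 4.6 and 5.7 for k = 5, 7 and 11 (simulation with 400,000 subjects per cell gave 5.8 for the last; the integral gives 5.74).

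**3. What would the by-visit mean add?**

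95% half-width at one visit with all 18 subjects = t(0.975, 17) × SD/√18 = 2.110 × SD/4.243:
- SD 15: 7.5 ms
- SD 20: 9.9 ms
- SD 25: 12.4 ms

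For a true 10 ms shift, the chance that this interval excludes zero is 0.76, 0.52 and 0.36. That is rough, but the mean does not drift upward as ECGs accumulate, its SD is reported beside it, and it is tied to a visit.

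**The case against.** The strongest case against is that little of consequence is lost.

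- **The safety endpoint is untouched.** A reader might infer that the primary safety objective of the AG-120 expansion is compromised. The documents do not support that. Protocol Table 2 defines Phase 1b safety and tolerability by type, frequency, seriousness, severity and relationship of adverse events, and SAP 11.1 keeps those tables for Phase 1b.
- **The QT-specific outputs survive.** A reader might infer that a QT effect of AG-120 would go unseen. It would not if it were large. The 480/500 ms and 30/60 ms categories of Protocol 9.7 are all in SAP 11.6 without a phase limit, and the QT management rules in Protocol 7.2.2.3.2 use the 480 and 500 ms thresholds.
- **AG-120 was not singled out.** SAP 11.4.1, 11.4.2, 11.4.5 and 11.5 assign by-visit change summaries for hematology, chemistry, lipids and vital signs to Phase 2 as well.
- **The SAP may refine the protocol.** Protocol section 9 calls itself an overview and leaves final methods to the SAP.
- **The added table is imprecise.** It would come from a single-arm cohort in which some QT-prolonging co-medication is allowed under monitoring (Protocol 8.1), and no dose rule or test would use it.

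All of this stands, and it sets the severity. It does not remove the point: the SAP excludes an output that the protocol plans, without a stated reason, and the exclusion falls wholly on the drug with the reported QT signal.

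**Conclusion.** The point holds as a minor one. In the SAP text available, AG-120 has no by-visit summary of QTcF or its change from baseline, although Protocol 9.7 plans one without a phase limit. Whether the missing SAP sections supply it cannot be settled from this text.

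The loss is confined to the size, spread and timing of smaller QTcF changes, around 10 ms. Larger shifts and individual threshold events remain visible.

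It would be tempting to say that the maximum-based count cannot distinguish a 10 ms shift from none, by setting 4.9 (10 ms, SD 15) against 5.9 (no shift, SD 25). That compares different assumed SDs. At equal SD the count does move (1.5 to 4.9, 3.8 to 7.5, 5.9 to 9.1). The supportable statement is that the count mixes shift, variability and number of ECGs.

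The textual finding needs no assumption. The magnitudes rest on the assumed SD of 15 to 25 ms, on independent normal readings and on 18 subjects with complete ECGs. No endpoint, test or dosing decision changes.

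**What to change.** In SAP 11.6, replace the restriction to treatment arms in Phase 2 with: *by dose cohort (Phase 1b, with the AG-120 + AZA total column of SAP 5.1) and by treatment arm (Phase 2)*. Do this at least for QTcF in AG-120, include change to the last visit as in Protocol 9.7, and state that the Phase 1b summary is descriptive only.

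The cost is one clause and a few extra tables from ECGs already collected. The numbers are small: about 18 subjects in the total column, fewer per cohort and at later visits, with the one-visit half-width of about 7.5 to 12.4 ms shown above. The total column is therefore the one to read. Applying the clause to all Phase 1b cohorts would also restore the summary for the AG-221 100 mg and 200 mg dose-finding cohorts.

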11.7. Echocardiogram/Multi-gated Acquisition

Data of echocardiogram (ECHO) and multi-gated acquisition (MUGA) measurements will be collected on the eCRF as part of the safety assessment. Data listing will be provided.

11.8. ECOG Performance Status

Shift tables will be provided for ECOG PS from baseline to worst values across all visits.

A by-subject listing will be presented for each phase of the study.

12. PHARMACOKINETIC ANALYSIS

The PK population will be used for all PK analyses.

12.1. Values below the Limit of Quantification or Missing

Pre-dose concentrations that are below the limit of quantification (BLQ) will be assigned a numerical value of zero for PK analysis. Post-dose concentrations that are BLQ and occur before the first quantifiable concentration will also be treated as zero for PK analysis. Post-dose concentrations that are BLQ but occur between two quantifiable concentrations will be treated as missing for PK analysis.

Concentrations assigned a value of missing will be omitted from the calculation of descriptive statistics. For concentration values that are BLQ, a concentration value of zero will be included for the computation of arithmetic mean, and a postdose zero concentration will be substituted with a 50% value of the lower limit of quantification, for the computation of geometric mean. If 50% or more of the values are BLQ at one time point, the mean, median, and geometric mean will be reported as BLQ, the maximum will be the greatest measurable value (or BLQ if no measurable values), and other descriptive statistics will not be calculated.

12.2. Plasma Sample Collection

Blood samples for intensive PK assessments of AG-221 in plasma will be collected at the following time points: predose (0 hour) and 2, 3, 4, 6, 8 and 24 hours post-dose in the first twelve subjects on C2D1 in each of treatment arms in Phase 2.

Blood samples for intensive PK assessments of AG-120 in plasma will be collected at the following time points: pre-dose and 0.5, 2, 3, 4 hours, 6, and 8 hours post-dose on Days 1 of Cycle 1 and 2 in Phase 1b.

Plasma concentrations of AG-221 or AG-120 will be summarized by nominal time points, including mean, standard deviation, % coefficient of variation (CV%), geometric mean, geometric CV%, minimum, median, and maximum. Mean (\pm standard deviation) plot of plasma concentrations will be presented in both linear scale and semi-logarithmic scale. Figure will be provided.

The subjects not being assessed for intensive PK in the AG-221 treatment arm during the Phase 2 segments will undergo sparse PK samples for measurement of AG-221 concentration. Listing of all sparse PK samples will be provided.

